8.3.4 ECOG

The ECOG assessment is to be performed according to the seminal paper Toxicity and Response Criteria of the Eastern Cooperative Oncology Group published in the American Journal of Clinical Oncology in 1982

8.3.5 Cardiac evaluations

8.3.5.1 Electrocardiograms

At screening a triplicate 12-lead ECG(s) will be obtained using an ECG machine that automatically calculates the heart rate and measures PR, QRS, QT, and QTc intervals. Holter ECG monitoring is acceptable to replace 12-lead ECG, provided the heart rate and measures PR, QRS, QT, and QTc intervals can be produced and entered in the eCRF.

During treatment, one 12-lead ECG(s) will be obtained at all dosing visits.

A triplicate 12-lead ECG is obtained at the End of Study visit at week 18 (+/- 14 days).

Triplicate ECGs include 3 individual ECG tracings obtained as closely as possible in succession, but no more than 2 minutes apart.

8.3.5.2 Echocardiographic evaluation of left ventricular function

At baseline: Echocardiography (LVEF and GLS) will be measured, unless an assessment has been performed within 2 weeks of screening.

During the trial, echocardiography (LVEF and GLS, if available) will be measured prior to administration of the 5th dose at week 12 (+/- 7 days).

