	 Total anti-HER2 Immunoglobulin titers in sera by enzyme-linked immunosorbent assay (ELISA). Isotyping of anti-HER2 Immunoglobulins in sera (e.g. IgM, IgG (IgG1-4), IgD, IgE, IgA). Exploratory Endpoints: Percentage of patients with measurable disease at baseline achieving Complete Remission (CR) or Partial Response (PR) according to RECIST 1.1 as assessed by the investigator during routine follow up. Percentage of patients with Disease Control Rate (DCR) according to RECIST 1.1 as assessed by the investigator during routine follow up. Progression free survival (PFS) in patients with Stable Disease (SD), or PR, at the time of first dosing of ES2B-C001 alone or in combination with the adjuvant according to RECIST 1.1. Disease-free survival (DFS) in patients with CR at the time of first dosing of ES2B-C001 alone or in combination with the adjuvant according to RECIST 1.1. Overall survival (OS). This dose escalation part will be conducted according to an adapted 3+3
Study Period	 design. For each patient enrolled, there will be a: Screening period between 1 and 28 days prior to the first dose ES2B-C001. An out-patient treatment period of 12 weeks; Safety follow-up for ~6 weeks following the last dose of ES2B-C001. An end-of-study visit.
Study Design	The trial is a first-in-human, phase I, open-label, dose-escalating trial to assess the safety and tolerability of ES2B-C001 combined with [adjuvant] or without [adjuvant], in patients with human epidermal growth factor receptor 2 (HER2) expressing metastatic breast cancer.

Clinical Study: ES2B-C001-S01 EU CT No.: 2024-516333-12-00

Clinical Study: ES2B-C001-S01 EU CT No.: 2024-516333-12-00

The decision to escalate the dose to the next dosing cohort or initiate the expansion part will be taken by the sponsor based on the data safety monitoring board (DSMB) recommendations. The DSMB will base their recommendations on an evaluation of accumulated safety data and, if available, on immunogenicity data (antibody titers), whenever 3 patients of a specific cohort have received at least one dose, and the last patient completed the DLT observation period of 8 weeks.

Enrollment will be fully staggered in each of the populations, meaning that an observation period of 3 weeks plus 24 hours is foreseen before the second patient is dosed in one cohort. Dosing of the next subject in each cohort should ideally not take place until 1 week after the preceding patient has received the first dose.

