4.3 Dose escalation

A DSMB will be appointed to oversee the trial. The composition and responsibilities of the DSMB is described in a dedicated charter, which will include additional instructions for the dose escalation procedure.

The decision to escalate the dose to the next dosing cohort or initiate the expansion part will be taken by the sponsor based on the DSMB recommendations. For the decision of dose escalation, AEs collected during the DLT period will be assessed by the DSMB. Other available data beyond the DLT evaluation period for all patients in the trial will also be assessed before a decision on escalation to the next dose level can be taken. Dose escalation rules will be based on the number of patients with AEs, specifically DLTs (Section 4.3.2). The DSMB will base recommendations on an evaluation of accumulated safety data and may include other available data, including data on immunogenicity (antibody titers) in their review.

Patients who discontinue for reasons other than toxicity before having DLT evaluable safety data may be replaced at sponsor's discretion.

A schedule of trial procedures is provided in Section 1.3. The administration of adjuvanted and non-adjuvanted ES2B-C001 is described in Section 6 and the trial assessments are described in Section 8.

The dose escalation will include 3 planned dose level cohorts with adjuvanted ES2B-C001 (Section 6.2).

Enrollment will be fully staggered in each of the populations, meaning that an observation period of 3 weeks plus 24 hours is foreseen before the second patient is dosed in one cohort. Dosing of the next subject in each cohort should not take place until 1 week after the preceding patient has received the first dose. Prior to dosing the second patient, safety and reactogenicity data from the previous patient will be discussed at a pre-dosing call between PI(s), CRO medical monitor, and

Clinical Study: ES2B-C001-S01 EU CT No.: 2024-516333-12-00

Sponsor. At subsequent administrations, pre-dosing calls will be scheduled if safety concerns warrant it. This will ensure an evaluation of safety prior to administration of the next patients.

Any safety concerns, such as potential DLTs and/or events that may meet a criterion for initiation of rescue medication, will be escalated to the DSMB who will review accumulated safety data and may provide recommendations for trial adjustments e.g., applying additional overnight stays for patients.

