4.3.1 Dose escalation rules

Dose escalation to a higher dose will be driven by an evaluation by the DSMB. At the time of DSMB evaluation, the last patient in the current dose level cohort must have received the 2nd dose and must have accumulated safety data for 8 weeks following the first dose. This allows for the DLT evaluation period to include an assessment of a potential delay in dose 2 due to toxicity concerns, as described for DLT number 5 in Section 4.3.2.

If one of the 3 patients in a dosing cohort experiences a DLT, 3 additional patients are added to the same dose level cohort. If 2 or more patients among these 6 patients experience DLTs, no further dose escalation can occur, and lower dose levels can be further explored. Dose escalation will continue until not more than 1 out of 6 patients experience DLT in a dose level cohort or the highest dose level group has completed treatment or no trial stopping criterion has been met. See Figure 2.

[figure not shown]

Figure 2: Dose-escalation according to a 3+3 design

Dose escalation will continue until not more than 1 out of 6 patients experiences a DLT in a dose level cohort (see DLT definitions in Section 4.3.2) or the dose level of

Clinical Study: ES2B-C001-S01 EU CT No.: 2024-516333-12-00

treatment has been completed (maximum administered dose MAD) or a trial stopping criterion has been met. The stopping criteria for dose escalation and trial are provided in Section 7.

Patients experiencing DLT will have their administration of adjuvanted or non-adjuvanted ES2B-C001 discontinued. These patients are allowed to remain in the trial to follow safety, disease progression and immune response. The DSMB will convene and recommend whether a re-start of these patients' treatment is advised and if a dose reduction may be required.

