4.3.2 Definition of Dose-limiting Toxicity (DLT)

A DLT is defined as any grade \geq 3 AE according to the NCI-CTCAE v. 5.0 observed at any time from the first administration of ES2B-C001 (alone or adjuvanted) to the 8 weeks thereafter, which despite standard supportive care and in the opinion of the Investigator, is possibly, probably, or definitely related to adjuvanted or non-adjuvanted ES2B-C001, or other event as described below. Investigators evaluation of relatedness to trial treatment administration should take concomitant medication into account.

DLTs will include:

- 1. Any grade ≥ 3 adverse events except:
 - a. Grade ≥ 3 nausea, vomiting, or diarrhea lasting ≤ 72hours with optimal medical therapy Grade 3 fatigue or anorexia lasting < 7 days.
 - b. Fever that occurs within 48 hours of IMP administration and resolves to Grade 2 within 48 hours and is fully resolved within 7 days.
 - c. Non-clinically relevant isolated biochemical abnormalities (e.g., isolated increase in gamma-glutamyltransferase [GGT]).
 - d. Laboratory values out of normal range without related clinical symptoms, clinically transient isolated in nature.
 - e. Laboratory abnormality that is asymptomatic and deemed by the Investigator not to be clinically significant.
- 2. Grade 3 autoimmune reactions, except Grade 3 autoimmune thyroiditis or other endocrine abnormality that can be managed by endocrine therapy.
- 3. Intolerable or > grade 3 injection-site reactions according to FDA guidance 2007 (table 16 appendix 2).
- 4. Grade 2 decrease in left ventricular ejection fraction (LVEF).
- 5. Treatment delay of >14 days due to any related adverse event(s).

In any case, the reported toxicity should be discussed between the Investigators and both the DSMB and the Sponsor. All toxicities will be graded using NCI-CTCAE Version 5.0 based on investigator assessment.

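### The LVEF criterion for a DLT closes at 8 weeks, but the only on-treatment echocardiogram in the legible text is at week 12, so a planned scan cannot trigger it

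*Protocol*

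**What the plan says.** Section 4.3.2 of the protocol defines a DLT as a related Grade 3 or higher event occurring "from the first administration of ES2B-C001 (alone or adjuvanted) to the 8 weeks thereafter", then adds "or other event as described below". Item 4 of its list is "Grade 2 decrease in left ventricular ejection fraction (LVEF"), with no time limit of its own.

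The 8 weeks recur wherever escalation is described. The synopsis (1.1) has the DSMB review a cohort once "the last patient completed the DLT observation period of 8 weeks". Section 4.3.1 says the last patient "must have accumulated safety data for 8 weeks following the first dose", and explains that this timing lets the DLT period take in a delayed second dose, which is item 5 of the list.

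Section 8.3.5.2 gives two occasions for LVEF: baseline, and one echocardiogram that "will be measured prior to administration of the 5th dose at week 12 (+/- 7 days"). Section 8.3 refers to the schedule of activities for all safety timepoints; that table is not legible here.

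On later findings, Section 4.3 says: "Other available data beyond the DLT evaluation period for all patients in the trial will also be assessed". Section 7.2.1 pauses treatment and refers the patient to cardiology for moderate or severe symptomless cardiac dysfunction, and Section 12.3 makes such dysfunction an event of special interest.

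**The concern.** A DLT criterion works only if the measurement behind it falls inside its window. Here the planned measurement comes after the window has closed. Section 2.3 presents cardiac monitoring as the safeguard against HER2-directed effects on normal heart tissue, yet the planned LVEF result has no place in the count that drives the trial.

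That count matters twice. Under 4.3.1 it decides whether to escalate, add three patients or stop: "If 2 or more patients among these 6 patients experience DLTs, no further dose escalation can occur". Under 9.3.1 it sets the MTD through a 33% line. A dose level could therefore pass as free of cardiac DLTs because nobody was due to look within 8 weeks, even if the week-12 scans then showed falls.

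**Working it through.** **Day convention.** Days are counted from first dose = 0. Check: week 18 = 18 × 7 = 126, which is study Day 127, the last immunogenicity sample in 8.2.1.

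**1. Window against scan.**
- Window closes (4.3.2): 8 × 7 = 56.
- Echocardiogram (8.3.5.2): 12 × 7 = 84, ± 7, so 77 to 91.
- Gap: 77 − 56 = 21 to 91 − 56 = 35 days. The visit allowance cannot bridge it.
- Stated on-treatment echocardiograms inside the window: 0 of 1.

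**2. Does the 8-week limit cover item 4?** Item 5 (treatment delay) is not defined by grade, so it too belongs to the additional events. Section 4.3.1 nevertheless places it inside the 8-week period. The synopsis speaks of one DLT period of 8 weeks, and 4.3 separates data from that period from data beyond it. Together these put item 4 under the 8 weeks as well.

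**3. What the DSMB can have seen.** The earliest review is 56 days after the last patient's first dose. For a patient first dosed *d* days before the last one, that is day *d* + 56 on that patient's own clock.
- Scan possible by then: *d* + 56 ≥ 77, so *d* ≥ 21.
- Scan certain by then: *d* + 56 ≥ 91, so *d* ≥ 35.
- Last patient: *d* = 0, so always 21 to 35 days short.

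Minimum stagger in 4.3 (22 days, then 7) gives first doses on days 0, 22 and 29:

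| Patient | First dose | Scan due |
|---|---|---|
| 1 | 0 | 77–91 |
| 2 | 22 | 99–113 |
| 3 | 29 | 106–120 |

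Review: 29 + 56 = day 85, with 0 or 1 of 3 scanned. If the next cohort starts that day without expansion, its first doses fall on days 85, 107 and 114. The first cohort's last scan (days 106–120) then comes when 1 to 3 patients have started the next level. The second escalation review is at 114 + 56 = day 170, which is 170 − 120 = 50 days after the first cohort's last scan is due. Slower accrual leaves fewer scans outstanding.

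**4. What one week-12 fall changes.**

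| Not counted | Counted | Action under 4.3.1 |
|---|---|---|
| 0/3 = 0% | 1/3 = 33.3% | escalate → add three patients |
| 1/6 = 16.7% | 2/6 = 33.3% | escalate → no further escalation |

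The second row crosses the 33% line in 9.3.1. In the first row 33.3% is provisional, because 4.3.1 expands the cohort to six; with no further DLT it becomes 1/6 = 16.7%.

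**5. Illustration.** Let *p* be the true rate of LVEF decreases meeting criterion 4. This is an assumption; the protocol gives no rate. Suppose all are symptomless, none is found by an unscheduled scan, and there is no other DLT. If they count, a level passes the 3+3 rule with probability (1−*p*)³ + 3*p*(1−*p*)² × (1−*p*)³: 0.906 at *p* = 0.10, 0.709 at 0.20 and 0.434 at 0.33. If they do not count, it is 1.0 at every *p*.

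**The case against.** The strongest reply is that patients are protected whatever the label. A week-12 fall goes to the DSMB under 4.3, is reportable within 24 hours as an event of special interest (8.4.1, 12.3), and if moderate or severe pauses dosing under 7.2.1. Under 10.7 the DSMB may add patients or recommend intermediate doses. Troponin and NT-proBNP are in the safety panel (8.3.6), and a persistent significant value must be explained, which could prompt an earlier scan. All of this stands, so a reader should not infer that a week-12 fall would be ignored. None of it puts the fall into the DLT count, and no legible text orders an LVEF measurement between baseline and week 12.

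The unread schedule of activities could list an earlier scan. That limits confidence. Section 8.3.5.2 reads as complete, however, and an extra scan would still leave the week-12 result outside the count.

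Three stronger readings are tempting and not supported:
- That the text leaves it evenly open whether a week-12 fall is a DLT, because the additional events follow the time clause and 9.3.1 sets no window. The treatment of item 5 in 4.3.1 points to exclusion.
- That 1/3 by itself fixes the MTD. Section 4.3.1 requires three more patients first.
- That cardiac toxicity is to be expected. The two Table 2 entries that report LVEF show no change.

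**Conclusion.** The point holds for the legible text. Criterion 4 has no stated scheduled measurement that can trigger it: the planned scan comes 21 to 35 days after the window closes, and on the better reading a fall found there is not a DLT for escalation or the MTD. One such event can turn escalation into expansion, or 1/6 into 2/6. At the first review, most of a fast-accruing cohort is unscanned in any case, so the main effect is on later escalation decisions and the MTD.

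This is worth fixing, with medium confidence. It assumes that the schedule of activities adds no earlier echocardiogram and that the DSMB charter, which is not shown, does not already settle the matter. A later SAP is not the place for it: Section 9 requires the SAP only before database lock, and the DLT definition is needed at each escalation.

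**What to change.** In 4.3.2, with matching wording in the synopsis and 4.3.1, state that:
- for criterion 4 the window runs from first dose through the planned week-12 echocardiogram;
- an LVEF decrease of Grade 2 or higher found there counts as a DLT for the MTD and for every escalation decision taken after it is known. Including higher grades keeps a Grade 3 fall at week 12 from escaping both item 1 and item 4;
- no new relatedness condition is added to item 4;
- each DSMB review reports how many week-12 echocardiograms are outstanding;
- if such a DLT takes a cleared level from 0/3 to 1/3, the existing 4.3.1 rule applies: three more patients at that level before it or a higher one is named the MTD;
- the 8-week timing of escalation reviews, and of DLT evaluability and replacement, is unchanged.

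This adds no scan and delays no review. The costs are that a level may be reclassified after 1 to 3 patients have started the next (fastest calendar), that the level may then need three more patients, and that a patient whose week-12 result counts has the fifth dose stopped under 4.3.1 unless the DSMB advises a restart. Patients unscanned at a review stay unscanned; this change does not close that gap.

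Closing it costs more and is the sponsor's choice. Waiting for every scan adds 21 to 35 days at each of two escalations (2 × 21 = 42 to 2 × 35 = 70 days in a planned 15-month study). An extra scan is an added procedure. Moving the scan earlier gives up LVEF data after later doses.

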8.3.6 Clinical Safety Laboratory Tests

Clinical laboratory tests will be performed by the laboratories mentioned in the study-specific Laboratory Manual. Samples will be collected in appropriate tubes and handled according to standard procedures of the applicable laboratory and according to the study-specific laboratory manual. Clinical laboratory variables will be determined as outlined in Table 13.

Table 13: Safety laboratory assessments

Clinical laboratory assessments				
Hematology	White blood cell (WBC) count Red blood cell (RBC) count Hemoglobin (Hb) Hematocrit (HCT) Mean corpuscular volume (MCV) Mean corpuscular hemoglobin (MCH) Platelet count	Lymphocytes (% and absolute) Neutrophils (% and absolute) Monocytes (% and absolute) Eosinophils (% and absolute) Basophils (% and absolute)		
Coagulation	Prothrombin time D-dimer Activated partial thromboplastin time			
Clinical chemistry	Alanine aminotransferase (ALT) Albumin Alkaline phosphatase (ALP) Aspartate aminotransferase (AST) Blood urea nitrogen (BUN) Calcium Creatinine Creatinine Kinase (CK) Troponin (T or I) Natriuretic peptides (NTproBNP)	Glucose Lactate dehydrogenase (LDH) Phosphorus Potassium Sodium Total bilirubin Uric acid C-reactive protein (CRP) Total protein		
Urinalysis	Bilirubin Blood Glucose Ketones Leukocytes Creatinine	pH Protein Specific weight Urobilinogen Nitrite Urine microscopic analysis (cells, bacteria, casts, crystals)		

Clinical Study: ES2B-C001-S01 EU CT No.: 2024-516333-12-00

- The investigator must review the laboratory results, document this review, and record any
 clinically significant changes occurring during the trial as an AE. The laboratory results must
 be retained with source documents.
- Abnormal laboratory findings associated with the underlying disease are not considered clinically significant unless judged by the investigator to be more severe than expected for the patient's condition.
- All laboratory tests with values considered clinically significantly abnormal during participation in the trial should be repeated until the values return to normal or baseline or are no longer considered clinically significant by the investigator or medical monitor.
 - If clinically significant values do not return to normal/baseline within a period of time judged reasonable by the investigator, the etiology should be identified, and the sponsor notified.
 - All protocol-required laboratory tests must be conducted in accordance with the laboratory manual and the SoA (Section 1.3).
 - o If laboratory values from non-protocol-specified laboratory tests performed at the institution's local laboratory require a change in patient management or are considered clinically significant by the investigator, then the results must be recorded as AEs.

8.3.7 Pregnancy Testing

Pregnancy testing is to be conducted with a highly sensitive serum or urine human chorionic gonadotropin (hCG) pregnancy test at screening and the days of vaccine administration as well as follow up visits (see Table 1 SoA). If pregnancy is suspected, additional pregnancy tests should be performed, and the result recorded in the patient's medical records. Local urine testing will be standard for the protocol unless serum testing is required by local regulation or IEC.

8.4 Adverse Events (AEs), Serious Adverse Events (SAEs), and Other Safety Reporting Progression of the breast cancer under trial is not considered an adverse event (AE) or serious adverse event (SAE) unless it results in hospitalization or death.

The definitions of AEs, AESIs and SAEs can be found in Appendix 1, Section 12.

The investigator and any qualified designees are responsible for detecting, documenting, and recording events that meet the definition of an AE or SAE and remain responsible for following up all reportable safety events.

The method of recording, evaluating, and assessing causality of AEs and SAEs and the procedures for completing and transmitting SAE reports are provided in Appendix 1, Section 12.

8.4.1 Time Period and Frequency for Collecting AE and SAE Information

All SAEs will be collected from start of first dose administration on day 1 (visit 2) until the follow-up visit at the timepoints specified in the SoA (Section 1.3). All reportable safety events that occur

Clinical Study: ES2B-C001-S01 EU CT No.: 2024-516333-12-00

after the consent form is signed but before the first administration of adjuvanted or non-adjuvanted ES2B-C001 will be recorded as medical history/current medical conditions, not as AEs.

All AEs occurring from the first administration of adjuvanted or non-adjuvanted ES2B-C001 must be reported by the investigator until the follow-up visit.

All SAEs and AESIs will be recorded and reported to the sponsor or designee immediately and under no circumstance should this exceed 24 hours, as indicated in Appendix 1, Section 12. The investigator will submit any updated SAE and AESI data to the sponsor within 24 hours of it being available.

All pregnancies from the time of first administration of adjuvanted or non-adjuvanted ES2B-C001 until the follow-up visit must be reported by the investigator.

Investigators are not obligated to actively seek information on AEs or SAEs after conclusion of the trial participation. However, if the investigator learns of any SAE, including a death, at any time after a patient has been discharged from the trial, and the investigator considers the event to be reasonably related to the trial intervention or trial participation, the investigator must promptly notify the sponsor.

